8.1.1. Incidence of Adverse Events

Summaries of the total number of TEAEs and the number of subjects with at least one TEAE will be provided by treatment group and total group. The number of subjects and the number of events will also be presented by SOC and PT/LLT. At each level of subject summarization, a subject is counted once if the subject reported one or more events. Percentage will be calculated out of the number of subjects in the Safety Set.

A summary of TEAEs will also be presented in descending order from the SOC with the highest total incidence (that is, summed across all treatment groups) to the SOC with the lowest total incidence. If the total incidence for any two or more SOCs is equal, the SOCs will be presented in alphabetical order. Within each SOC, the PTs/LLTs will be presented in alphabetical order.

All AEs will be presented in a listing.

8.1.2. Relationship of Adverse Events to Study Drug

A summary of TEAEs by relationship to study drug will be presented in a table. The investigator will provide an assessment of the relationship of the event to the study drug. The possible relationships are “Not Related”, “Possible”, “Probable”, and “Definite”. In the TEAE relationship table, if a subject reports multiple occurrences of the same TEAE, only the most closely related occurrence will be presented. Treatment-emergent AEs that are missing a relationship will be presented in the summary table as “Definite” but will be presented in the data listing with a missing relationship. Percentages will be calculated based on the number of subjects in the Safety Set.

The TEAE data will be categorized and presented by SOC, PT/LLT, and relationship in a manner similar to that described in [Section 8.1.1](#).

8.1.3. Severity of Adverse Event

A summary of TEAEs by severity will be presented in a table. The severity that will be presented represents the most extreme severity captured on the CRF page. The possible severities are “Mild”, “Moderate”, “and “Severe”. In the TEAE severity table, if a subject reported multiple occurrences of the same TEAE, only the most severe will be presented. Treatment-emergent AEs that are missing severity will be presented in the table as “Severe” but will be present in the data listing with a missing severity. Percentages will be calculated out of the number of subjects in the Safety Set.

The TEAE data will be categorized and presented by SOC, PT/LLT, and severity in a manner similar to that described in [Section 8.1.1](#).

AE's severity will be rated using CTCAE 4.03. Each CTCAE 4.03 term is a Medical Dictionary for Regulatory Activities (MedDRA) Lowest Level Term (LLT). The CTCAE displays Grades

1-5 with unique clinical descriptions of severity of each AE. TEAE will be summarized by maximum CTCAE grade. Percentages will be calculated out of the number of subjects in the Safety Set.

The TEAE data will be categorized and presented by SOC, PT/LLT, and CTCAE grade in a manner similar to that described in [Section 8.1.1](#).

8.1.4. Serious Adverse Events

The seriousness of an AE should be assessed by the Investigator independently from the severity of the AE. A serious AE (SAE) is defined as any untoward medical occurrence that at any dose results in death, is life-threatening, is a congenital anomaly/birth defect, requires in-patient hospitalization or prolongation, or results in significant disability/incapacity.

Important medical events that may not result in death, be life-threatening, or require hospitalization may be considered SAEs when, based upon medical judgment, they may jeopardize the subject and may require medical or surgical intervention to prevent one of the outcomes listed above.

Serious treatment-emergent adverse events (SAEs) will be presented in a table. Treatment-emergent SAEs by relationship to study drug will be presented in a table. A treatment-related treatment-emergent SAE is a treatment-emergent SAE with any relation to study drug other than “Not Related”. Treatment-emergent SAEs that are missing a relationship will be presented in the table as “Related” but will be presented in the data listing with a missing relationship. At each level of subject summarization, a subject is counted once if the subject reported one or more events. Percentages will be calculated out of the number of subjects in the Safety Set.

The treatment-emergent SAE data will be categorized and presented by SOC and PT/LLT in a manner similar to that described in [Section 8.1.1](#) and by severity as described in [Section 8.1.3](#).

8.1.5. Adverse Events Leading to Treatment Discontinuation

A summary of TEAEs with a study drug action taken of “Drug Withdrawal” will be presented in a table. At each level of subject summarization, a subject is counted once if the subject reported one or more events. Percentages will be calculated out of the number of subjects in the Safety Set within the subgroup category.

The summary of TEAEs with a study drug action taken of “Drug Withdrawal” will also be presented in descending order of frequency from the SOC with the highest total incidence (that is, summed across all treatment groups) to the SOC with the lowest total incidence. If the total incidence for any two or more SOCs is equal, the SOCs will be presented in alphabetical order. Within each SOC, the PTs/LLTs will be presented in alphabetical order.

8.1.6. Adverse Events Leading to Study Discontinuation

All subjects who have an AE with the answer to “Caused Study Discontinuation” is “Yes” will be presented in a listing.

8.1.7. Death

All subjects who have an AE with an outcome of “Death Related to Adverse Event” will be presented in a listing.

8.2. Clinical Laboratory Evaluations

Observed values and absolute change from Baseline for routine chemistry, hematology, and urinalysis values will be summarized by treatment group and overall at each per-protocol time point for subjects in the Safety Set.

All relevant clinical laboratory tests in chemistry and hematology will be classified as Low, Normal, and High, or Normal/Abnormal according to the normal ranges. This categorical data will be summarized in shift tables comparing the extreme results at each scheduled post-baseline visit with those at the Baseline visit. Extreme post-baseline results will also be summarized. When there are multiple values within a visit for a particular laboratory variable, the worst value will be taken (worst being the smallest value for criteria below a certain threshold or the largest value for criteria above a certain threshold). If a subject has a value below the threshold and above the threshold, the value furthest from the threshold will be chosen.

In data listings, laboratory values will be compared to normal ranges; out-of-range and clinically significant laboratory values will be identified.

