5 SUBJECT SELECTION

5.1 INCLUSION CRITERIA

Patients who meet the following criteria may be included in the study:

1. Males and females between 18 and 75 years of age inclusive who are able to comprehend instructions and follow the study procedures, and are willing to sign an Informed Consent Form (ICF).
2. Confirmed diagnosis of PSC based any **two** of the following three criteria:
 - a. Historical evidence of an elevated ALP > ULN from any laboratory
 - b. Liver biopsy consistent with PSC
 - i. Patients with small-duct PSC on liver biopsy must also have a concurrent diagnosis of IBD
 - c. Abnormal cholangiography consistent with PSC as measured by MRCP, ERCP, or percutaneous transhepatic cholangiography
3. Subjects must have certain additional laboratory parameters in specified ranges at Screening, as follows:
 - a. ALP > 1.5 × ULN
 - b. Total bilirubin ≤ 2.5 mg/dL
 - c. ALT and AST < 5 × ULN
 - d. Serum creatinine < 2 mg/dL or creatinine clearance > 60 mL/min by Cockcroft-Gault calculation
 - e. Platelets ≥ 100 K/uL
 - f. International Normalized Ratio (INR) ≤ 1.3 (in the absence of warfarin or other anticoagulant therapy)
 - g. Carbohydrate antigen 19-9 (CA19-9) ≤ 130 U/mL
 - i. Patients with a CA 19-9 > 130 U/mL may be enrolled if they have two results a minimum of 4 weeks but not greater than 1 year apart and not more than 50 U/mL difference between the two results
4. Patients taking UDCA will be allowed to enroll if meeting the following criteria:
 - a. Total daily dose of < 27 mg/kg/day
 - b. Minimum of 12 weeks of treatment
 - c. No significant dosage changes during 8 weeks prior to Screening
 - d. Minimum of 12-week washout period prior to Screening if UDCA is stopped

5. Patients with concomitant IBD are allowed to enroll upon meeting the following criteria:
 - a. A colonoscopy within 12 months of Screening with no evidence of dysplasia
 - b. No episode of an IBD flare or IBD flare-related bloody diarrhea within 6 months of Screening and through Day 1
 - c. Stable regimen of biologic treatments, immunosuppressive, or systemic corticosteroids (< 10 mg/day) for > 12 weeks prior to Screening and through Day 1
 - i. Vedolizumab is an excluded biologic treatment
6. Female patients are eligible for the study if they meet the following criteria:
 - a. Are not pregnant or nursing

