5.3 DISCONTINUATION OF STUDY TREATMENT IN AN INDIVIDUAL SUBJECT

Study treatment will be discontinued if any of the following CTCAE categories or abnormal elevations in liver function tests occurs on-treatment:

- Any Grade 3 TEAE related to study drug
- Any Grade 4 or higher TEAE
- Elevation of ALT **and** total bilirubin > 2 times above subject-specific baseline value calculated using the median of the Screening and Day 1 value
 - ALT, AST, and total bilirubin must be re-tested within 72 hours.
 - Subjects with persistent elevations should be discontinued from treatment, independent of whether or not they are symptomatic.
- Elevation of ALT > 2 times above subject-specific baseline
 - ALT, AST, and total bilirubin must be re-tested within 72 hours.
 - Subjects with persistent elevations who are asymptomatic may continue treatment under protocol-defined *close observation* criteria.
 - Subjects with persistent elevations who are symptomatic must discontinue treatment.
 - Subjects continuing treatment under *close observation* should implement study procedures and assessments as part of the study conduct:
 1. Repeat liver enzyme and serum bilirubin tests two or three times weekly. The frequency of retesting can decrease to once a week or less if abnormalities stabilize or the trial drug has been discontinued and the subject is asymptomatic.
 2. Repeat additional tests to evaluate liver synthetic function (e.g., INR, direct bilirubin) as appropriate.
 3. Obtain a detailed history of symptoms and prior or concurrent diseases.
 4. Obtain a history of concomitant drug use (including nonprescription medications and herbal and dietary supplement preparations), alcohol use, recreational drug use, environmental toxin exposure, and special diets.
 5. Rule out acute viral hepatitis and other acute or chronic hepatobiliary diseases.

Dose reductions or increases are not allowed as part the study conduct.

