2.3. Treatments

Subjects will be instructed to self-administer/dose at approximately the same time each morning in the whole treatment period. Blinded study drug (NGM282 or placebo) will be administered as a subcutaneous (SC) injection in the abdomen. Subjects will be trained on self-administering a

SC injection. Self-administration will occur in clinic under the observation of clinic staff on weeks 1, 2, 4, 8, and 12.

3. General Statistical Considerations

Continuous data will be summarized using descriptive statistics (i.e. n, mean, standard deviation, median, minimum, and maximum). Categorical data will be summarized using the subject count and percentage in each category. For the summary statistics of all numerical variables, unless otherwise specified, minimum and maximum will be displayed to the same level of precision as the reported data. Mean and median will be displayed to one level of precision greater than the data collected. Standard deviation/standard error will be displayed to two levels of precision greater than the data collected. P-values will be rounded to three decimal places. If a p-value is less than 0.001 it will be reported as “<0.001.” If a p-value is greater than 0.999 it will be reported as “>0.999.”

Data will be displayed in all listings sorted by treatment group. Subjects will be identified in the listings by the subject identification number concatenated with the investigator number.

When count data are presented, the percentage will be suppressed when the count is zero in order to draw attention to the non-zero counts. The denominator for all percentages will be the number of subjects in that treatment within the analysis set of interest, unless otherwise specified.

Unless otherwise specified, Baseline will be defined as the last non-missing evaluation prior to or on the date of study drug SC injection (Day 1).

The study day will be calculated as follows:

If the assessment date occurs on or after the date of NGM282 SC injection (Day 1):

Study day = assessment date – date of NGM282 SC injection (Day 1) + 1.

If the date of interest occurs before the date of NGM282 SC injection (Day 1):

Study day = assessment date – date of NGM282 SC injection (Day 1)

[figure not shown]
There is no study day 0.

For all efficacy analyses, analysis visit windows will be used for assigning assessments to an analysis visit, as follows:

Scheduled Visit	Target Day	Visit Window (Days)
Screening	-42 to -1	Not applicable

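### The normal-range shift tables in SAP 8.2 cannot show worsening of liver tests already High at Baseline, and no planned table counts the protocol 5.3 liver signal by arm

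*SAP*

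**What the plan says.** SAP 8.2 sorts laboratory results by reference range: "All relevant clinical laboratory tests in chemistry and hematology will be classified as Low, Normal, and High, or Normal/Abnormal according to the normal ranges". It continues: "This categorical data will be summarized in shift tables comparing the extreme results at each scheduled post-baseline visit with those at the Baseline visit". The liver tests are not named, and protocol 8.10.2 makes shift tables optional for parameters that the SAP is to identify. The natural reading is that liver chemistry counts as relevant.

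On entry values, protocol 5.1 requires Screening ALP above 1.5 x ULN (criterion 3a). The other liver limits are ceilings only: "Total bilirubin ≤ 2.5 mg/dL" (3b) and "ALT and AST < 5 × ULN" (3c).

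Protocol 5.3 judges liver worsening during treatment on a different scale: "Elevation of ALT > 2 times above subject-specific baseline", and separately ALT together with total bilirubin. The reference there is the median of the Screening and Day 1 values. SAP section 3 uses another reference: "Baseline will be defined as the last non-missing evaluation prior to or on the date of study drug SC injection". The SAP does not derive the 5.3 baseline.

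SAP 8.2 also plans other laboratory output: "Observed values and absolute change from Baseline for routine chemistry, hematology, and urinalysis values will be summarized by treatment group", and "Extreme post-baseline results will also be summarized".

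**The concern.** A three-level scale with an open top category cannot register a rise in someone who starts in that category. In this population that is practically everyone for ALP and an unknown share for ALT, AST and bilirubin. The protocol takes account of abnormal starting values by setting its on-treatment signal relative to each subject's own baseline. The analysis plan does not carry that scale into any table.

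This SAP describes itself as the interim plan. Under protocol 8.10.9 the interim takes place when about 24 subjects (at least 8 per arm) have completed Week 12, and safety and efficacy then inform whether the study continues. With so few subjects per arm, the useful liver information is how many individuals rose, by how much, and whether ALT and bilirubin rose in the same person. The planned tables do not give those counts.

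**Working it through.** The plan states no figure for the shift tables, so there is nothing to reproduce. The check applies the SAP 8.2 categories to values in multiples of ULN.

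**Inputs**
- Category: High if the value exceeds 1 x ULN, otherwise Normal (SAP 8.2).
- Entry limits: protocol 5.1, criteria 3a to 3c.
- Signal: value/baseline > 2, reading the 5.3 wording as a ratio.
- Arm sizes: 20 randomised (protocol 8.1); at least 8 at the interim (protocol 8.10.9).

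Let *b* be the baseline in multiples of ULN and *m* the fold change. A worsening shift is visible only if *b* ≤ 1 and *b* × *m* > 1.

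**1. ALP.** With *b* > 1.5, *b* × *m* > 1 for every *m* ≥ 1. Examples: 1.51 × 2 = 3.02; 2 × 3 = 6; 5 × 3 = 15. All are High to High. The only visible move is normalisation. A subject could have a Normal ALP Baseline only if ALP fell by at least 1 − 1/1.5 = 33% between Screening and Day 1. That is possible, but not usual for a population selected on raised ALP.

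**2. ALT/AST above ULN at Baseline.** For *b* = 1.2, 2, 3 and 4.9 with *m* = 2.01, 3 and 5, all twelve combinations stay High to High. Examples: 1.2 × 5 = 6.0; 4.9 × 2.01 = 9.85.

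**3. ALT/AST normal at Baseline.** A rise of *m* = 2.01 is visible if *b* > 1/2.01 = 0.498. So 0.5 × 2.01 = 1.005 reads Normal to High, while 0.4 × 2.01 = 0.804 stays Normal. A just-over-2-fold rise therefore shows as a shift only for baselines from about 0.5 to 1.0 x ULN.

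**4. Ordering.** 4.8/1.2 = 4.0-fold gives no shift; 1.1/0.9 = 1.22-fold gives a worsening shift.

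**5. How many subjects can show an upward ALT shift.** The documents do not give the share normal at Baseline, so the shares below are assumed.

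| Assumed share normal | Can shift, of 20 | Cannot shift, of 20 | Can shift, of 8 |
|---|---|---|---|
| 0% | 0 | 20 | 0 |
| 10% | 2 | 18 | 0.8 |
| 25% | 5 | 15 | 2 |
| 50% | 10 | 10 | 4 |
| 75% | 15 | 5 | 6 |

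The same logic applies to AST and bilirubin. The documents give no ULN for bilirubin; subjects can enter above it wherever the laboratory limit is below 2.5 mg/dL.

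**6. What the continuous summaries add.** A subject rising from 1.2 to 4.8 x ULN changes by 3.6 x ULN. That moves the arm mean by 3.6/20 = 0.18 x ULN, or 3.6/8 = 0.45 x ULN at the interim. SAP section 3 includes the minimum and maximum, so the rise could appear as the largest change. But a 3.6 x ULN rise is a 4.0-fold change from 1.2 and only (4.8 + 3.6)/4.8 = 1.75-fold from 4.8. The maximum change does not tell these apart and does not count subjects.

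**7. On the 5.3 scale**, taking *b* as the 5.3 baseline. ALT rises of 1.2 to 4.8 (ratio 4.0), 4.9 to 9.85 (2.01) and 0.4 to 0.804 (2.01) are all counted. A rise of 0.9 to 1.1 (1.22) is not.

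**The case against.** The strongest reply is that the shift table is only one of several outputs.
- SAP section 3 reports minimum and maximum, so the largest value and largest rise per arm and visit will be seen.
- SAP 7.2 models percent change from Baseline in ALP, ALT, AST, bilirubin and GGT, which is a baseline-relative scale. ALP is also the primary endpoint, so its uninformative safety shift loses little.
- SAP 8.1.3 tabulates TEAEs by maximum CTCAE grade, SAP 8.1.5 tabulates those leading to drug withdrawal, and the listings flag out-of-range and clinically significant values. With about 24 subjects at the interim, reading the listings is feasible.

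Most of this stands, and it means a single large outlier would probably not go unseen. It does not close the gap. The percent-change models give group estimates in the FAS, not counts in the Safety Set. TEAE grading depends on an event being reported. Protocol 5.3 lets asymptomatic subjects with a persistent isolated ALT rise continue under close observation, so the withdrawal table need not include them. Listings give no comparison by arm.

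A reader might infer that the tables cannot show liver worsening at all. The documents do not support that, because ALT, AST and bilirubin may be normal at entry and those subjects can shift to High. A reader might also take the summary of extreme results to follow the same Low/Normal/High classes. That is plausible, but SAP 8.2 does not say so; it refers to thresholds without defining them.

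**Conclusion.** The point holds in limited form. The SAP 8.2 shifts cannot show worsening of ALP in practically any subject, nor of ALT, AST or bilirubin in subjects already above ULN at Baseline. For ALT, that second group is 20 to 5 of 20 per arm over the assumed range of 0% to 75% normal. Partial coverage exists elsewhere, but no planned table counts by arm the subjects who meet the protocol's own signal, alone or jointly with bilirubin.

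This rests on three assumptions: that liver chemistry is among the relevant tests, that the 5.3 wording means a ratio above 2, and that Screening and Day 1 ALP seldom differ by a third or more.

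It is tempting to extend the conclusion to the final safety analysis. The documents do not support that: SAP section 1 describes the interim analysis, and SAP section 10 mentions a full-study SAP that is not among the documents. Nor do they show that a liver signal would be missed, only that these tables would not count it. This is a worthwhile, low-cost improvement rather than a fault that invalidates the safety analysis.

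**What to change.** Keep the Low/Normal/High shifts, since Normal-to-High moves are informative. Add to SAP 8.2 one Safety Set table by arm, with counts and percentages:
- subjects whose maximum post-baseline ALT exceeds 2 x the subject-specific baseline of protocol 5.3 (median of Screening and Day 1);
- subjects with ALT and total bilirubin both above 2 x that baseline, stating whether both must occur in the same sample;
- the distribution of the maximum post-baseline/baseline ratio for ALP, AST, GGT and total and direct bilirubin. Display bands such as ≤1, >1–1.5, >1.5–2, >2–3 and >3 are illustrative; only the 2 x level comes from the protocol, and there only for ALT and total bilirubin.

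Name the liver tests covered, say whether unscheduled retests count towards the maximum, and define the thresholds for the summary of extreme results.

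The cost is one derived baseline and one table, from chemistry already collected at every visit. The lower bands will be noisy because the maximum is taken over up to six post-baseline visits (Weeks 1, 2, 4, 8, 12 and 16). The change affects reporting only; the rules in protocol 4.1 and 5.3 stay as they are.

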8.9.2 Analysis of Primary Efficacy Endpoint

As the primary efficacy analysis, the population mean change in ALP from Baseline to Week 12 will be compared between treatment groups using a mixed-effect model repeated measures (MMRM) analysis of covariance (ANCOVA) of the primary efficacy endpoint, using the FAS. The model will contain treatment group, visit, treatment group by visit interaction, UDCA (yes/no), treatment group by UDCA interaction, and diabetic status as classification variables and the Baseline value as a continuous covariate. An unstructured covariance matrix will be assumed; however, if the modeling using that matrix does not converge, then other matrices will be explored. For each treatment and treatment comparison versus placebo, the least squares mean, associated standard error (SE), 95% confidence interval, and corresponding p-value will be presented. The overall type 1 error rate for the two primary comparisons versus placebo will be controlled using the step-down Dunnett multiple-testing procedure ([Dmitrienko and D'Agostino 2013](#)).

As secondary analyses within the same MMRM, the linear combinations

$$\mu_1 - \mu_3$$

and

$$(\mu_1 + \mu_3)/2 - \mu_p$$

will be estimated, where μ_1 , μ_3 , and μ_p are the population LS means for the primary efficacy endpoint of the 1 mg NGM282, 3 mg NGM282, and placebo groups, respectively.

Further explanatory variables may be included in additional modeling using the FAS, similar to the primary efficacy analysis, depending on the relevance to the endpoint; such modeling will be specified in the SAP.

If strong evidence of marked deviations from normality is noted in the distribution of the residuals of the primary MMRM ANCOVA, then FAS analyses using data transformations of the primary efficacy endpoint, and/or non-parametric approaches, will be explored.

As sensitivity analyses,

- a. The primary analysis for the primary endpoint will be repeated for the PPS.

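### The laboratory tie rule in SAP 8.2 drops one of two out-of-range results when a subject has both a low and a high value, and its threshold and distance scale are undefined

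*SAP*

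**What the plan says.** SAP 8.2 has chemistry and hematology results "classified as Low, Normal, and High, or Normal/Abnormal according to the normal ranges". Two outputs follow. The first is by visit: "This categorical data will be summarized in shift tables comparing the extreme results at each scheduled post-baseline visit with those at the Baseline visit". The second is one short sentence: "Extreme post-baseline results will also be summarized".

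Two selection rules then appear in sequence.

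- For repeats: "When there are multiple values within a visit for a particular laboratory variable, the worst value will be taken", with worst defined by direction as "worst being the smallest value for criteria below a certain threshold or the largest value for criteria above a certain threshold".
- For subjects with results on both sides: "If a subject has a value below the threshold and above the threshold, the value furthest from the threshold will be chosen".

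The same section flags out-of-range and clinically significant values in the listings. Protocol 8.10.2 leaves the choice of shift tables to the SAP and contains no rule of this kind.

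**The concern.** A two-limit classification has two possible kinds of abnormality, and a subject can have both. The definition of worst handles this without a tie-break: the smallest value answers the low criterion and the largest answers the high one. The last sentence undoes that by keeping a single value, so a real out-of-range result leaves the table.

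The rule also cannot be programmed as written. It speaks of one threshold where there are two, gives no distance scale (raw units, percent of the limit, or fold), and does not say whether it applies within a visit or over the whole post-baseline period. Two programmers could classify the same subject in opposite ways.

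At stake is the number of subjects per arm reported with a Low or a High extreme. Arms are small: one subject is 1/20 = 5% of a planned arm and 1/8 = 12.5% of the minimum arm at the interim analysis (Protocol 8.10.9). The SAP introduction describes this plan as the interim one, and SAP section 10 says that the Data Monitoring Committee receives a subset of the interim and full-study outputs.

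**Working it through.** The plan gives no figure to reproduce. Neither document gives reference ranges or within-subject variability, so every range and variance below is an assumption.

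**1. When is the low value dropped?** Let LLN and ULN be the lower and upper limits. Write the low value as f × LLN (f < 1) and the high value as m × ULN (m > 1). Measuring each value from its own limit, the low value is dropped when:

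- raw units: m·ULN − ULN > LLN − f·LLN, that is m > 1 + (1 − f)(LLN/ULN);
- percent of own limit: m − 1 > 1 − f, that is m > 2 − f;
- fold: m > 1/f.

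| f | raw units, LLN/ULN 0.3 to 0.9 | percent of own limit | fold |
|---|---|---|---|
| 0.5 | m > 1.15 to 1.45 | m > 1.50 | m > 2.00 |
| 0.7 | m > 1.09 to 1.27 | m > 1.30 | m > 1.43 |

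**2. One pair, different answers.** Assume a range of 3.5 to 5.0 and a subject with 2.5 and 6.2.

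- Raw units, own limit: 3.5 − 2.5 = 1.0 against 6.2 − 5.0 = 1.2. High is kept.
- Percent of own limit: 1.0/3.5 = 28.6% against 1.2/5.0 = 24.0%. Low is kept.
- Fold: 3.5/2.5 = 1.40 against 6.2/5.0 = 1.24. Low is kept.
- Literal single threshold: from the ULN, 2.5 against 1.2 keeps Low; from the LLN, 1.0 against 2.7 keeps High.

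With 2.5 and 5.5, the raw distances from the own limits are 1.0 and 0.5, so Low is kept and the high result is lost. The rule can discard either side.

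**3. Is there a tilt?** Only on a scale that creates one. In raw units, a non-negative analyte cannot lie more than LLN below its lower limit, so any value above ULN + LLN beats every low value, zero included. In a simulation of 400,000 subjects with six values each (right-skewed lognormal, log-SD 0.35), the raw-unit rule kept High in roughly 78% to 85% of subjects with both excursions. The lowest figure rests on only 54 such subjects. On a fold scale the same model is symmetric, and the split is about even.

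**4. How often does it matter?** Hematology and chemistry are scheduled at Weeks 1, 2, 4, 8, 12 and 16, giving six post-baseline values. Take a reference range holding 95% of values. With independent values, P(at least one low and at least one high) = 1 − 2(0.975⁶) + 0.95⁶ = 1.7%. Simulated values with intraclass correlation (ICC):

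| Assumption | P(both), per analyte |
|---|---|
| ICC 0.3 | about 0.2% |
| ICC 0.5 | about 0.01% to 0.02% |
| ICC 0.5, within-subject SD × 1.5 | about 2.0% |
| ICC 0.5, within-subject SD × 2 | about 12% |

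Per analyte, 0.02% of 60 subjects is 0.012 subject; 2% is 1.2 subjects of 60, or 0.48 of the 24 at the interim. The 12% row is a stress case with no support in the documents. All these frequencies pool values across visits, so they apply to the extreme-results summary only.

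**5. Which table is exposed?** The repeat-value rule is limited to a visit; the tie rule says only that a subject has both values. If the tie rule is confined to a visit, both excursions must occur in that visit, where the schedule has one sample. If it runs over the post-baseline period, the extreme-results summary loses one direction for every subject with both. In the by-visit shift table, a low at one visit and a high at another each still appear at their own visit.

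**The case against.** The strongest reply is that this is loose wording with little practical effect. Much of that stands.

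- **Direction.** A reader might infer that the rule systematically hides clinically important low values. The text names neither direction nor scale, and it keeps the low value whenever that is the further one. The tilt towards High follows only if distance is taken in raw units. Clinical importance plays no part in the rule.
- **Other outputs.** A reader might also infer that only the listings would show the lost value. SAP 8.2 summarizes observed values by arm and time point, and SAP section 3 includes the minimum and maximum in such summaries. Separate-visit excursions remain in the by-visit shifts. Protocol 7.1 counts clinically relevant adverse laboratory changes as adverse events, which SAP 8.1.3 tabulates by maximum CTCAE grade.
- **Population.** It is tempting to argue that swings in both directions are likely here because the protocol admits subjects on a "Stable regimen of biologic treatments, immunosuppressive, or systemic corticosteroids" and its primary model has "diabetic status as classification variables". The support is thin: the regimen must have been stable for more than 12 weeks before Screening, platelets must be at least 100 K/uL at Screening, and the SAP model omits diabetic status.
- **Frequency.** Repeat testing within a visit is not scheduled. The frequent retesting in Protocol 5.3 concerns liver enzymes and bilirubin.

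What the reply does not remove is the stated instruction to choose one value. None of the other outputs gives the number of subjects per arm whose post-baseline extreme was Low, or High, against Baseline.

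**Conclusion.** The point holds as a minor one. The rule discards one of two out-of-range results, contradicts the direction-specific definition beside it, and leaves the threshold, distance scale and scope open. The internal conflict rests on the SAP text alone; the sizes rest on assumed ranges and variability.

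The likely effect is an undercount of Low or High extremes for a few subjects at most, mainly in the extreme post-baseline summary if the rule is applied across visits. The by-visit shift table is touched only by two excursions within one visit. The documents do not support a claim that low values are systematically suppressed or lost from the report. The primary analysis, type I error and power are unaffected.

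**What to change.** Delete the tie-rule sentence from SAP 8.2. For each analyte with a two-sided range, tabulate two results against Baseline separately: the lowest value (Low / not Low) and the highest value (High / not High). Apply this both within a visit and over all post-baseline values, and state that a subject with both excursions counts in both.

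This makes the tables follow the SAP's own definition of worst and removes the need for a threshold or distance scale. It needs no new data and no protocol change. The cost is a wording edit and one extra panel per table. A subject may appear in both panels, so their counts should not be added; a footnote can say so.
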